### 4 INVESTIGATIONAL PLAN

# 4.1 Overall Study Design

This is an open-label, multicenter Phase II study of oral BBI608 administered with Cetuximab, or Panitumumab, or Capecitabine to patients with advanced metastatic colorectal cancer. The study is based on a Simon 2-stage design that will examine the safety, tolerability and pharmacokinetics of BBI608 and Cetuximab, or Panitumumab, or Capecitabine, and assess the preliminary anti-tumor activity of BBI608 when administered in combination with Cetuximab, or Panitumumab, or Capecitabine in patients with advanced colorectal cancer.

BBI608 treatment will be at a dose level of 480 mg twice daily (960 mg total daily dose). In each cycle, BBI608 will be taken daily continuously for 4 weeks (28 days). BBI608 will be administered twice daily approximately one hour prior to or two hours after meals with the first dose given in the morning and approximately 12 hours between doses.

For patients receiving Cetuximab therapy, Cetuximab will be administered IV on day 5 of cycle 1 at 400 mg/m² intravenous infusion over 120 minutes as the initial dose, then weekly at 250mg/m² over 60-minutes at subsequent cycles.

For patients receiving Panitumumab therapy, Panitumumab will be administered IV on day 8, and 22 of each 28 day cycle at 6 mg/kg over 60 minutes.

For patients receiving Capecitabine therapy, Capecitabine will be administered orally at 1000 mg/m^2 bid daily on days 8-21 every three weeks.

Cycles will be repeated until progression of disease, unacceptable toxicity, or another discontinuation criterion is met. In the case of toxicity, adjustment is permitted. If administration of Cetuximab, or Panitumumab, or Capecitabine is discontinued due to Cetuximab, or Panitumumab, or Capecitabine-related toxicity, administration of BBI608 will be continued until disease progression if tolerated.

Initially, 6 patients will be enrolled in each combination arm at a dose level of 480 mg twice daily (960 mg total daily dose) BBI608. If  $\leq 1$  out of 6 patients has an observable DLT in the combination regimen, then that arm of the study will continue to enroll patients at 480 mg po twice daily (960 mg total daily dose) of BBI608 following the Simon 2-stage design (see Table 1). If

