## 7.1.3 Cetuximab, Panitumumab, or Capecitabine Administration

- Detailed instructions for the preparation, premedication, and administration of Cetuximab, Panitumumab, or Capecitabine are provided in the Product Labels approved by Health Canada or US FDA.
- Cetuximab will be administered via IV on Days 5, 12, 19 and 26 of a 28 day cycle, about 3 hours after the first daily dose of BBI608. Panitumumab will be administered via IV on Days 8, and 22 of a 28 day cycle, about 3 hours after the first daily dose of BBI608. Capecitabine will be administered orally twice-daily for two weeks out of three weeks. The first dose of Capecitabine should be taken about 3 hours after the first daily dose of BBI608 on day 8 of each 3 week cycle of Capecitabine.

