Medical history will be coded by SOC and PT using the MedDRA version 18.0 prior to the analysis. Medical history will be summarized by SOC and PT using the number and percentage of patients

for the safety analysis set.

Duration of Overall Survival Follow-up

The duration of overall survival (OS) follow-up is defined as time from the date of first treatment to death or the last known alive visit. The median follow-up time for OS and the corresponding 95% confidence interval (using the method of Brookmeyer and Crowley, 1982 with the log-log transformation) will be summarized using the reverse Kaplan-Meier (KM) method for the safety set. The analysis involves the event and censoring rules to be switched (ie, the patients who die become 'censored', and the censored patients are treated as the 'event').

Summaries of the number and percentage of patients who have died, those still in survival followup, those lost to follow-up, and those who have withdrawn consent will be also provided.

Extent of Exposure

Exposure may be summarized as dose received (cumulative dose or actual dose intensity) or as dose received relative to the intended dose (relative dose [RD], or relative dose intensity [RDI]), or both.

The information that will be summarized depends on how the study drug is dosed (eg, infusion cyclical, oral daily, oral cyclical).

In what follows, "time unit" can be weeks or days.

Actual treatment duration = actual end of treatment date – date of first dose of study drug + 1, where

- For napabucasin and Capecitabine, the actual end of treatment date is the last dosing date
- For cyclic combination drugs in Arms A and B, actual end of treatment date = last dose of cyclic dosing + interval 1, where interval = 7 for Arm A and interval =14 for Arm B.

Cumulative dose in a cycle or overall is the sum of the actual doses received in a cycle or overall, respectively.

Actual Dose Intensity [DI]

- By cycle actual DI (*dose unit/week*) = [cumulative dose in the cycle]/ [actual cycle duration in *weeks*]
- Overall actual DI (*dose unit/week*) = [overall cumulative dose] / [actual treatment duration in *weeks*]
- Note that actual DI for cyclical dosing is calculated based on actual cycle duration in all but the last cycle where it is fixed at the intended duration.

Relative Dose Intensity (RDI): The basic intent is to evaluate dose per *time unit* factoring in dose reductions, interruptions, or delays.

Relative dose intensity (RDI) by cycle and overall

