- Intended DI (*dose unit/time unit*) = [intended cumulative dose per cycle] / [intended number of *time units* in a cycle]
- By cycle RDI (%) = $100 \times [by cycle actual DI] / [intended DI]$
- \circ Overall RDI (%) = 100 × [overall actual DI] / [intended DI]

Note the intended dose level is fixed at the start of treatment rather than the start of a cycle

- One exception is for Cetuximab. For Cetuximab, dose level is permitted to change from 400 mg/m^2 on day 5 in cycle 1 to 250 mg/m² for each subsequent infusion. If dose level decreases for Cetuximab 4-7 days after first dose date, then updated dose level is the new intended dose level for Cetuximab.
- Second exception is for all backbone therapies. All backbone therapies incorporate BSA or weight to calculate each dose. Panitumumab incorporates weight to calculate each dose-all other therapies incorporate BSA. Therefore, the BSA to be used for calculating each dose of the backbone therapies will be using the Mosteller method (see below) based on the last available weight and height prior to each infusion. For Panitumumab, the last available weight prior to each infusion will be used for calculating each dose.
- $BSA [m^2] = ((Height [cm] \times Weight [kg])/3600) \times 0.5$
- Calculated doses will be rounded to the nearest integer
- Cumulative dose, actual dose intensity and relative dose intensity will remain missing if they cannot be derived due to missing weight, or BSA. Height from the most recent earlier visit can be used if height is missing.

The intended cumulative dose of napabucasin per cycle is calculated by (intended dose level per day) \times (intended cycle duration in days)

• Intended dose level per day for napabucasin is 500mg po BID

Dose unit of napabucasin is mg, dose unit of other combination drugs (except Panitumumab) is mg/m^2 , dose unit of Panitumumab is mg/kg.

Treatment compliance

Treatment compliance for napabucasin is defined as follows:

(Cumulative actual total dose / total planned or intended dose) $\times 100 = \%$ compliance

For any IV combination drug (Cetuximab and Panitumumab), compliance will be calculated using the following equation:

(Number of treatments administered / number of treatments that should have been administered) $\times 100 = \%$ compliance

For oral combination drug (Capecitabine), compliance will be calculated using the following equation:

(Cumulative actual total dose / total planned or intended dose) \times 100 = % compliance

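### The SAP's 4-7 day condition on cetuximab's planned dose step can make fully delivered cetuximab score about 72% (cycle 1) and 62.5% (later cycles) on relative dose intensity

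*SAP*

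**What the plan says.** The general rule for RDI in SAP 8.2.1 (Extent of Exposure) is: "Note the intended dose level is fixed at the start of treatment rather than the start of a cycle". Cetuximab is the first listed exception. The SAP describes its planned course as 400 mg/m² on Day 5 of cycle 1, changing "to 250 mg/m² for each subsequent infusion", and then gives the operative rule: "If dose level decreases for Cetuximab 4-7 days after first dose date, then updated dose level is the new intended dose level".

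Three things are left unsaid:

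- which drug's first dose starts the 4-7 day count;
- what happens when the planned step falls outside those days;
- whether the new level also covers the first infusion of cycle 1 or applies only from the second.

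On the protocol side, section 4.1 states "Cetuximab will be administered IV on day 5 of cycle 1 at 400 mg/m² intravenous infusion over 120 minutes as the initial dose", and section 7.1.3 states "Cetuximab will be administered via IV on Days 5, 12, 19 and 26 of a 28 day cycle". The cetuximab schedule in Appendix A gives the cycle 1 visits a window of ±1 day. Its footnote counts study days from the first BBI608 (napabucasin) dose.

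**The concern.** The SAP says RDI is meant to reflect reductions, interruptions and delays. The step from 400 to 250 mg/m² is none of these, because it is the planned regimen. Yet the SAP treats it as planned only if it falls in a window whose upper limit equals the nominal interval between the first two infusions. The rule therefore tolerates an early second infusion but no lateness, although the protocol permits both.

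Two patients given identical cetuximab doses, both within the protocol's windows, can then be measured against different denominators for the rest of treatment. A reader of the Arm A exposure table could take a group of patients at about 63-72% as evidence of cetuximab reductions that never happened. Because the anchor and the reach of the updated level are unstated, two programmers could also produce different tables from the same data.

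**Working it through.** The documents state no RDI figure, so there is none to reproduce. The steps below apply the SAP's formulas to a patient who receives every planned infusion in full.

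**Inputs**
- First infusion 400 mg/m², each later one 250 mg/m² (SAP 8.2.1). The protocol speaks of weekly 250 mg/m² at subsequent cycles; I follow the SAP's wording.
- Infusions on Days 5, 12, 19 and 26 of each 28-day cycle (Protocol 7.1.3).
- Visit window ±1 day (Protocol Appendix A).
- RDI = 100 × actual dose intensity / intended dose intensity. Actual intensity is cumulative dose over weeks. Intended intensity is intended cumulative dose per cycle over intended weeks in a cycle (SAP 8.2.1).
- Cetuximab treatment ends at the last infusion plus the interval of 7 days minus 1 (SAP 8.2.1; I read the missing sign as a minus).

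**Does the step fall in the 4-7 day window?**
- *Counted from the first cetuximab dose.* Nominal gap: 12 − 5 = 7 days, so the rule just fires. With the first infusion on Day 4, 5 or 6 and the second on Day 11, 12 or 13, the gap runs from 11 − 6 = 5 to 13 − 4 = 9 days. Gaps of 8 and 9 miss the rule.
- *Counted from the first napabucasin dose.* Nominal gap: 12 − 1 = 11 days. The earliest in-window second infusion gives 11 − 1 = 10 days. No in-window patient triggers the update.

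**RDI by cycle** (nominal 4-week cycles)
- Delivered in cycle 1: 400 + 3 × 250 = 1150 mg/m². Delivered in each later cycle: 4 × 250 = 1000 mg/m².
- Update missed, intended 4 × 400 = 1600: cycle 1 = 1150/1600 = 71.9%; later cycles = 1000/1600 = 62.5%.
- Update made and applied to the whole of cycle 1, intended 4 × 250 = 1000: cycle 1 = 1150/1000 = 115%; later cycles = 1000/1000 = 100%.
- Update made and applied only forward, intended 1150 then 1000: 100% in every cycle.

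**Overall RDI after k cycles** = (1150 + 1000(k − 1)) / (4k × intended level), with duration counted from the first cetuximab dose:

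| Cycles | Infusions | Delivered (mg/m²) | Update missed (400) | Update made, whole of cycle 1 (250) |
|---|---|---|---|---|
| 1 | 4 | 1150 | 71.9% | 115.0% |
| 2 | 8 | 2150 | 67.2% | 107.5% |
| 3 | 12 | 3150 | 65.6% | 105.0% |
| 4 | 16 | 4150 | 64.8% | 103.75% |

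**Sensitivity to duration.** From Day 5 to Day 26 + 6 = Day 32 is 28 days. If duration starts at napabucasin Day 1 it is 32 days, and one-cycle overall RDI becomes 1150/(32/7)/400 = 62.9% or 1150/(32/7)/250 = 100.6%. Over four cycles (116 days) the figures are 62.6% and 100.2%. With infusions on Days 4, 12, 19 and 26, duration from the first cetuximab dose is 29 days, and the missed-update overall value is 1150/(29/7)/400 = 69.4%.

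**Share of patients affected.** The documents give no data on visit timing. If both visits vary independently and uniformly over their three permitted days (assumption), the nine combinations give gaps of 5, 6, 7, 8 and 9 days with frequencies 1, 2, 3, 2 and 1, so 3/9 = 33% miss the update. If infusions keep to the same weekday (assumption), the gap is 7 days and the share is near 0. Both figures count from the first cetuximab dose.

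**The case against.** The strongest reply is that the rule works for a patient treated on the nominal days. Counted from the first cetuximab dose, the step comes at exactly 7 days and the update is made. That stands. A reader might infer that every fully dosed patient scores either 62.5-72% or 115%. The documents do not support this: the low figures need a gap of 8 days or more, or a count from napabucasin, and an updated patient scores 100% in every cycle after the first.

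It can also be said that an updated level naturally applies from the change onward, which gives 100% throughout. The text does not exclude this. Against it, the SAP defines a single intended dose intensity for both by-cycle and overall RDI. A forward-only reading needs two values (1150/4 = 287.5 and 1000/4 = 250 mg/m² per week) and gives no rule for which divides the overall figure. The formula favours the whole-cycle reading, and with it 115%, but the text does not settle it.

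The reach of the problem is also limited. A reader might infer that the table decides whether napabucasin can be combined with full-dose cetuximab. No section says so: arm continuation rests on DLT counts (SAP 4.2.1), and RDI is one of several optional exposure summaries. A reader might also infer that it enters the response evaluable set, and so DCR, through the 80% compliance criterion. The daily compliance defined in SAP 8.2.1 counts napabucasin days, and cetuximab compliance counts infusions. Neither uses the intended cetuximab dose level, nor do cumulative dose and actual dose intensity.

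**Conclusion.** The gap is real and should be corrected. The window for recognising the planned step does not match the protocol's visit windows under either reading of the anchor, and the SAP has no rule for a planned step outside it. One permitted day's difference can move an identically dosed patient from 100% to 62.5% in every later cycle. In cycle 1 the move is to 71.9%, from 100% or 115% depending on how far back the updated level applies.

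The by-cycle figures assume full delivery and nominal cycle lengths. The overall figures also take duration from the first cetuximab dose. How many patients are affected cannot be determined from the documents; the 33% is an illustration, not an estimate.

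The consequence is confined to the descriptive cetuximab RDI summary in Arm A. Infusion-count compliance, DCR, ORR, PFS and OS are unaffected, and the study tests no hypothesis.

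**What to change.** In SAP 8.2.1, remove the 4-7 day condition and set the cetuximab RDI denominator by infusion number from the schedule already planned: 400 mg/m² for infusion 1 and 250 mg/m² for each later infusion. The intended cumulative dose is then 1150 mg/m² in cycle 1 and 1000 mg/m² in each later four-infusion cycle. For overall RDI, divide the actual dose intensity by the summed planned dose over the planned duration.

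State also that cetuximab treatment duration runs from the first cetuximab dose. Otherwise a fully dosed one-cycle patient would score 28/32 = 87.5% even with the corrected denominator. With both changes, full delivery on the nominal days scores 100% in each cycle and overall (for example, 4150 delivered against 4150 planned over 16 weeks).

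The cost is a short SAP edit and a simple programming rule. No new data are needed. Only the analysis denominator and the duration convention change, not any dose given.

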2.1.2. Secondary Objectives

The secondary objectives of this study are as follows:

- To determine the pharmacokinetic profile of napabucasin and cetuximab, or panitumumab, or capecitabine when administered in combination.
- To determine the pharmacodynamics (biomarkers) of napabucasin.
- To evaluate tolerability of two dosing regimens of napabucasin by comparing administration of napabucasin at a 240 mg twice daily starting dose and escalating to 480 mg twice daily after Cycle 1 versus administration of napabucasin at a 480 mg twice daily starting dose with dose adjustment permitted.
- To evaluate tolerability of napabucasin by comparing prophylactic administration of anti-diarrheal medication versus as-needed administration of anti-diarrheal medication. The tolerability will be assessed using the adverse event profile and achieved dose intensity.

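### The SAP names the Mosteller body surface area but prints a multiplication by 0.5 where the square root belongs, which would distort BSA-based cetuximab and capecitabine exposure

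*SAP*

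**What the plan says.** The rule is in SAP 8.2.1, in the part on extent of exposure and relative dose intensity. The SAP states that the BSA used for each partner-drug dose "will be using the Mosteller method (see below) based on the last available weight and height prior to each infusion". The formula that follows is "Height [cm] \times Weight [kg])/3600) \times 0.5", with an explicit multiplication sign before 0.5 and no root or exponent.

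The same section sets the reach of that formula:

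- On which drugs use it: "Panitumumab incorporates weight to calculate each dose-all other therapies incorporate BSA". That leaves cetuximab and capecitabine.
- On units: "Dose unit of napabucasin is mg, dose unit of other combination drugs (except Panitumumab) is" mg/m², with panitumumab in mg/kg.
- Overall RDI is 100 times "overall actual DI] / [intended DI".
- Cumulative dose, actual dose intensity and RDI stay missing when they cannot be derived for want of weight or BSA.

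No other place in either document gives a BSA formula. Protocol 7.1.5 says only that BSA is calculated before each cycle from actual height and weight.

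**The concern.** The method named and the formula printed are different functions of height and weight. The number 0.5 belongs to Mosteller as an exponent; here it is a multiplier. A programmer who follows the printed line gets a BSA whose error depends on body size, so it is not a constant factor that cancels between patients.

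At stake are the descriptive exposure tables for cetuximab and capecitabine: cumulative dose and actual dose intensity in mg/m², RDI, and capecitabine compliance if it is computed through mg/m². RDI is meant to show reductions, interruptions and delays. With the printed formula, a smaller patient whose dose was reduced could appear fully dosed, and a larger patient given every dose could appear under-dosed.

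**Working it through.** **Inputs.** The printed formula, the drugs that use it, the units and the RDI definition come from SAP 8.2.1. The Mosteller definition is the standard one: BSA = √(height in cm × weight in kg / 3600). The documents contain no worked BSA, mg/m² dose or RDI, so there is no planned figure to reproduce. They also give no body sizes, so the heights and weights below are assumptions that show the range.

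**Step 1: the algebra.** Let x = H × W / 3600. True BSA is √x, so x = BSA². The printed value is 0.5 × x = BSA² / 2. Printed divided by true is therefore BSA / 2. This equals 1 only when BSA = 2.0 m², that is, when H × W = 14,400.

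**Step 2: numbers.** For 170 cm and 70 kg, x = 11,900 / 3600 = 3.306. The square root is 1.818 m² and the printed value is 1.653, a ratio of 0.909.

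| Assumed height, weight | Square root (m²) | As printed | Printed / true | Inverse, 2/BSA |
|---|---|---|---|---|
| 150 cm, 45 kg | 1.369 | 0.938 | 0.685 | 1.461 |
| 160 cm, 60 kg | 1.633 | 1.333 | 0.816 | 1.225 |
| 170 cm, 70 kg | 1.818 | 1.653 | 0.909 | 1.100 |
| 180 cm, 80 kg | 2.000 | 2.000 | 1.000 | 1.000 |
| 190 cm, 110 kg | 2.409 | 2.903 | 1.205 | 0.830 |

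**Step 3: from BSA to RDI.** The SAP does not say where BSA enters the ratio. There are three readings:

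- (a) Milligrams given are divided by BSA and compared with the nominal mg/m². RDI is multiplied by 2/BSA.
- (b) Milligrams given are compared with nominal mg/m² × BSA. RDI is again multiplied by 2/BSA.
- (c) The same BSA enters both sides, or mg/m² is recorded directly. BSA cancels or is not needed, and RDI is unaffected.

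Under (a) or (b), a patient given every planned milligram has RDI = 100 × 2/BSA:

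| True BSA (m²) | 1.5 | 1.6 | 1.8 | 2.0 | 2.2 | 2.4 |
|---|---|---|---|---|---|---|
| RDI at full dosing | 133% | 125% | 111% | 100% | 91% | 83% |

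**Step 4: can it hide a reduction?** The protocol's own reduction steps serve as illustrations. Capecitabine at 75% (Protocol 7.2.3) at 1.5 m² reads 0.75 × 1.333 = 100%. Cetuximab at 200 instead of 250 mg/m² (Protocol 7.2.1, rash table) is 0.80 of the intended dose, and at 1.6 m² it reads 0.80 × 1.25 = 100%. In the other direction, a fully dosed patient at 2.4 m² reads 83%, an apparent shortfall of 17 percentage points.

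**The case against.** Four points can be made on the other side.

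**It may be a typographical or extraction slip.** The SAP names Mosteller, so a programmer may well use the square root, and text extracted from a PDF can lose an exponent. This stands as a reason to look at the source page first. Against it, the extracted line keeps the superscript in m² and shows an explicit multiplication sign, which a lost superscript would not normally produce. If the page does print a multiplication, correct code would disagree with the SAP, so the text still needs changing.

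**BSA may cancel.** Reading (c) cannot be excluded. The SAP treats BSA as an exception to the rule on the intended dose level, yet also gives the dose unit as mg/m². The rule that leaves RDI missing when BSA is missing points towards (a) or (b) but does not settle it. The RDI percentages are therefore conditional.

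**Most exposure measures contain no BSA.** This stands in full. For the study drug, "Intended dose level per day for napabucasin is 500mg po BID" is a fixed milligram dose. Panitumumab goes by weight under the SAP rule. (Protocol 7.1.5 describes panitumumab dosing as BSA-based, against mg/kg in Protocol 4.1; those passages must be reconciled, but that is a separate matter.) Compliance for the infused drugs is "Number of treatments administered / number of treatments that should have been administered", a count. A reader might infer that every RDI in the study is wrong; the documents do not support that.

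**The tolerability objective is not reached.** A reader might connect this error to SAP 2.1.2, where "The tolerability will be assessed using the adverse event profile and achieved dose intensity". That objective compares napabucasin starting doses and anti-diarrheal strategies. Its natural dose-intensity measure is napabucasin's, in milligrams. The sub-cohort measures in Protocol 10.8, days of diarrhea and capsule compliance, contain no BSA either. The link should not be drawn.

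**Conclusion.** As written, the formula is not the method it names. The discrepancy factor is exact: printed BSA is BSA/2 times the true value. It is zero at 2.0 m² and grows with distance from it; at 175 cm and 80 kg, for example, the factor 2/BSA is only 1.014.

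The consequence is limited to cetuximab and capecitabine exposure derived through BSA, and to capecitabine compliance if it is computed through mg/m². For RDI, the range of 133% to 83% over 1.5 to 2.4 m² rests on three assumptions: the line is programmed as printed, BSA enters one side of the ratio only, and patients have the body sizes assumed here.

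A reader might also infer that patients were misdosed. The documents do not show this: the formula is an analysis derivation, and the protocol prints no BSA formula. Disease control rate, objective response rate, progression-free survival, overall survival and the dose-limiting toxicity rule contain no BSA term. This is a minor correction to descriptive partner-drug exposure tables.

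**What to change.** 1. Check the SAP source page to see whether an exponent was lost.
2. If the multiplication is really there, replace the line with BSA [m²] = √((Height [cm] × Weight [kg]) / 3600).
3. Add one sentence saying whether cetuximab and capecitabine doses are recorded in mg or mg/m², and whether BSA enters the actual or the intended side of the RDI ratio. Say the same for capecitabine compliance.
4. Confirm that the exposure programs use the square root, and rerun the affected tables if they do not.

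The cost is one corrected line, one clarifying sentence and a short code check. There is no trade-off.

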2.1. Study Design

This is an open label, multi-center, Phase II study of napabucasin (BBI608) administered in combination with either cetuximab, or panitumumab, or capecitabine to patients with advanced colorectal cancer. The study is designed to explore the safety, tolerability, preliminary anti-tumor activity and pharmacokinetics of napabucasin when administered in combination with each one of the above regimens.

Six patients would be initially enrolled in each combination arm at a napabucasin dose level of 500 mg BID (1000 mg total daily using 50 mg capsules) before protocol amendment 2 or 480 mg twice daily (960 mg total daily dose) using 80 mg capsules after protocol amendment 2. If ≤ 1 out of 6 patients had an observable dose limiting toxicity (DLT) in the combination regimen, then that arm of the study would continue to enroll patients at 500 mg BID (1000 mg total daily) using 50 mg capsules or 480 mg BID (960 mg total daily) using 80 mg capsules following a Simon 2-stage design. If a DLT occurred in ≥ 2 of the 6 patients in a combination arm, then that arm of the study would be closed and no further patients would be enrolled. A given arm of napabucasin in combination with cetuximab, or panitumumab, or capecitabine would continue to enroll patients if no more than 1 out of 6 patients in the combination arm had an observable DLT.

The number of colorectal cancer patients enrolled would be based on a two-stage Simon design and is presented in Section 4.1 of the protocol amendment 2 [5]. If any of the three arms reach a disease control rate (DCR) of 60% or higher at the end of the Simon Stage 2 portion of the study, a one-time option to expand accrual to a total sample size of up to 50 patients may be implemented for each arm.

To evaluate the tolerability of napabucasin, patients from each arm would be assigned to one of 4 sub-cohorts (with 6 patients in each sub-cohort: IA, IB, IIA, IIB) from protocol amendment 2. The evaluation of tolerability would be done at selected centers for the study arm that was continuing patient accrual and in which a total of 50 evaluable patients had not been reached. For each

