combination arm, patients assigned to sub-cohorts IA and IB would receive napabucasin at 240 mg twice daily (480 mg total daily dose) starting on Day 1 of Cycle 1. Intra-patient dose escalation of napabucasin to 480 mg twice daily (960 mg total daily dose) was allowed for patients in these cohorts as tolerated. Patients assigned to sub-cohorts IIA and IIB would receive napabucasin at 480 mg twice daily (960 mg total daily dose) starting on Day 1 of Cycle 1. In the event of toxicity, dose adjustment of napabucasin was permitted, as recommended in dose modification guidelines. Additionally, patients assigned to sub-cohorts IA and IIA would receive prophylactic anti-diarrheal treatment starting the day prior to Day 1 of Cycle 1. Patients assigned to sub-cohorts IB and IIB would receive anti-diarrheal treatment on an as-needed basis starting with development of diarrhea (ie, any occurrence greater than the patient's baseline). For each combination regimen, patients would be sequentially assigned to each of the 4 sub-cohorts in the following order until 6 patients were accrued in each of the sub-cohorts: IA, IB, IIA, and IIB. If required, up to an additional 20 patients might be assigned to selected sub-cohorts to validate the observations in the initial 6 patients.

Sub-cohort	Napabucasin Starting Dose Level	Anti-diarrheal Administration*
IA	240 mg bid (480 total daily dose) ¹	Prophylactic
IB	240 mg bid (480 total daily dose) ¹	As needed
IIA	480 mg bid (960 total daily dose) ²	Prophylactic
IIB	480 mg bid (960 total daily dose) ²	As needed

Table 1 Tolerability Analysis of Napabucasin

¹Intra-patient dose escalation of napabucasin to 480 mg po twice daily (960 mg total daily dose) is allowed as tolerated. ²In case of toxicity, dose adjustment of napabucasin is permitted.

*See protocol amendment 2 [5] section 7.1.4 for details

A study cycle would consist of 28 days of daily administration of napabucasin in combination with cetuximab or panitumumab, or capecitabine. Cycles would continue until unacceptable toxicity, disease progression (clinical or radiological) or another discontinuation criterion is met. Pharmacokinetic (PK) assessments would be performed on the first 6 patients enrolled in each combination arm. Pharmacodynamic assessments would be performed in patients with readily accessible tumor tissue through an optional tumor biopsy. Evaluation of anti-tumor activity would be performed at 8-week intervals per RECIST 1.1 while patients remain on study.

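### A single 500 mg BID reference for napabucasin relative dose intensity makes fully adherent patients on the amendment 2 doses read below 100%

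*SAP*

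**What the plan says.** SAP 8.2.1 defines RDI as 100 times actual dose intensity (DI) divided by intended DI, both by cycle and overall. Its stated purpose is dose per unit of time "factoring in dose reductions, interruptions, or delays". For napabucasin the only reference value is "Intended dose level per day for napabucasin is 500mg po BID". A note in the same section sets the intended level once, when treatment begins. The two exceptions listed concern cetuximab and the backbone therapies, not napabucasin.

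SAP 2.1 describes three assigned starting levels:

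- 500 mg BID (1000 mg per day) before amendment 2.
- "480 mg twice daily (960 mg total daily dose) using 80 mg capsules after protocol amendment 2".
- In the tolerability sub-cohorts, "patients assigned to sub-cohorts IA and IB would receive napabucasin at 240 mg twice daily (480 mg total daily dose" for IA and IB, with 480 mg BID for IIA and IIB.

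The sub-cohorts were planned "with 6 patients in each sub-cohort: IA, IB, IIA, IIB) from protocol amendment 2", so no sub-cohort patient was assigned 500 mg BID.

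Escalation in IA/IB is described in two ways. SAP 2.1 says that it "was allowed for patients in these cohorts as tolerated". SAP 2.1.2 describes the regimen as "240 mg twice daily starting dose and escalating to 480 mg twice daily after Cycle 1". SAP 2.1.2 also says: "The tolerability will be assessed using the adverse event profile and achieved dose intensity".

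**The concern.** RDI normally tells the reader how much of the assigned treatment a patient received, and 100% means all of it. Here the denominator is a dose that patients entering after amendment 2 were not assigned. An IA/IB patient with perfect adherence would appear in the exposure table at about half the intended intensity in cycle 1, and an IIA/IIB patient slightly short of full. A reader of the clinical study report would naturally take those figures as toxicity-driven reductions or missed doses. Because SAP 8.2 summarizes data by arm and sub-cohort, the difference between 48% and 96% would sit side by side in a study that sets out to compare the tolerability of the two starting regimens. The figures would reflect the design, not tolerability.

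**Working it through.** The documents state no RDI value, so there is no figure to reproduce. The check applies the SAP's own formula.

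**Inputs**
- Intended dose: 500 mg BID = 1000 mg/day (SAP 8.2.1; the daily total is given in SAP 2.1).
- Cycle: 28 days = 4 weeks (SAP 2.1).
- Assigned doses: 500 mg BID = 1000 mg/day, 480 mg BID = 960 mg/day, 240 mg BID = 480 mg/day (SAP 2.1).
- Assumptions: every assigned dose is taken, cycles last exactly 28 days, and escalation, where it occurs, is on day 1 of cycle 2.

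**Intended DI** = 1000 × 28 / 4 = 7000 mg/week.

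**RDI as the SAP is written**

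| Assigned and fully taken | Actual DI (mg/week) | RDI |
|---|---|---|
| 500 mg BID | 1000 × 7 = 7000 | 7000/7000 = 100% |
| 480 mg BID | 960 × 7 = 6720 | 6720/7000 = 96% |
| 240 mg BID, one cycle or never escalated | 480 × 7 = 3360 | 3360/7000 = 48% |
| 240 then 480, two cycles | (3360 + 6720)/2 = 5040 | 72% |
| 240 then 480, three cycles | (3360 + 2 × 6720)/3 = 5600 | 80% |
| 240 then 480, four cycles | (3360 + 3 × 6720)/4 = 5880 | 84% |

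By cycle, the escalated patient reads 48% and then 96%. The two-cycle row matches the period over which Protocol 10.8 analyses the sub-cohorts for diarrhea days and compliance. The overall value rises with longer treatment.

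**What other IA/IB denominators would give over two cycles**
- Own starting dose only: escalated after cycle 1, 5040/3360 = 150%; never escalated, 3360/3360 = 100%.
- Escalation after cycle 1 counted as planned: escalated, 5040/5040 = 100%; never escalated, 3360/5040 = 67%.

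The IA/IB figure therefore depends heavily on a rule that the SAP does not state.

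**The case against.** The strongest defence is that a common reference is deliberate: it keeps delivered dose comparable between the 240 and 480 mg BID starts, whereas denominators based on the assigned dose would bring both to 100%. The SAP does not give that reason, and actual DI in mg/week already provides a common scale. A measure meant to reflect reductions, interruptions and delays should not show a shortfall when there were none. This defence does not remove the inconsistency.

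Other objections do limit the point:

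- **The secondary objective.** A reader might infer that the comparison of dosing regimens is compromised. It is not. The objective names achieved dose intensity, and actual DI uses no intended dose. SAP 8.2.1 also leaves it open whether exposure is summarized as dose received, as relative dose, or both.
- **Visibility of departures.** A reader might infer that RDI as written cannot reveal departure from the assigned regimen. That is too strong. Full adherence gives known constants (96% at 480 mg BID, 48% in a 240 mg BID cycle), RDI by cycle separates patterns that the overall figure merges, and the SAP plans separate compliance summaries.
- **The note that the level is set when treatment begins.** A constant 500 mg BID also satisfies it, so no contradiction is proved. If the note means each patient's own starting dose, it disagrees with the 500 mg BID line.
- **Response-evaluable set and compliance.** A reader might infer that the 80% compliance rule in SAP 6.3 is distorted too. The documents do not say that its dose level is 500 mg BID. Protocol 7.3 and 10.8 calculate compliance per dose level, and SAP 8.2.1 reports daily compliance by dose-level cohort. The undefined dose terms in SAP 6.3 and in the compliance text of 8.2.1 are missing detail, not demonstrated errors.

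**Conclusion.** The inconsistency is real, and following the stated rule gives a misleading figure. For patients assigned the amendment 2 doses, RDI under full adherence is 96% or 48%, with 72% overall only for exactly two cycles with escalation at cycle 2. Patients treated at 500 mg BID before amendment 2 correctly read 100%. RDI is thus not comparable across dose cohorts as a measure of adherence to the assigned regimen.

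The consequence is small. The gap at 480 mg BID is 4 percentage points. The larger gap is confined to IA/IB, whose research questions Protocol 10.8 calls exploratory. SAP 4.1 plans no hypothesis tests, and no endpoint or decision rule is shown to use RDI. The documents do not give the number of patients actually treated at each level, so the effect on any pooled summary cannot be sized. This is a minor correction to a descriptive exposure summary.

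**What to change.** 1. Reconcile the 500 mg BID line in SAP 8.2.1 with SAP 2.1. Replace the single value with the level assigned at entry under the patient's protocol version and sub-cohort. Do not lower it for toxicity reductions, so that these remain visible.
2. For IA/IB, reconcile the two descriptions of escalation in SAP 2.1 and 2.1.2. Then state one analysis denominator for all IA/IB patients, whether or not they escalate, and say in the table footnote what full adherence gives under it.
3. Show RDI by cycle as well as overall.
4. Report actual DI in mg/week by sub-cohort beside RDI, and use actual DI for the comparison of regimens.
5. As a clarification, say in one line which dose level the compliance terms in SAP 6.3 and 8.2.1 refer to.

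The cost is SAP wording and a programming change, with no new data. The proposal concerns analysis denominators only and endorses no clinical dose or escalation rule.
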